2.2. Treatment groups

- ACP-01
- Placebo

2.3. Subgroups

Depending on the sample size, the following subgroups will be explored: region, race, gender, age, and baseline prognostic factors (e.g., presence of ulcers at baseline and ulcer size at baseline).

3. STATISTICAL METHODS

3.1. General considerations

The following descriptive statistics will be provided depending on the nature of considered data:

Qualitative data: number of observed values, number and percentage of subjects per class.

Quantitative data: number of observed values, mean and standard deviation, median, first and third quartiles, minimum and maximum.

Descriptive summary statistics (n, mean (SD), median, min and max) will be provided for variables measured on a continuous scale.

The frequency distribution (n, %) will be provided for variables measured on a nominal scale.

3.2. Study subjects

Description of disposition of subjects (status, protocol deviations and analysis set) and baseline characteristics will be performed by treatment arm and overall.

3.2.1. Disposition of subject

Subject disposition will be tabulated for each treatment arm and overall by summarizing the number and percentage of subjects who are randomized, treated with the study treatments ACP-01 or placebo, included in each analysis set, and by the reason for early discontinuation (AE/SAE, major violation of study protocol, withdrawal of consent, lost to follow-up, death, suspected pregnancy, or other).

3.2.2. Demographic and baseline characteristics

Demographics and baseline data will be described for the mITT analysis set. Subject demographics and baseline characteristics, including underlying disease history, medical history and prior medications will be compared between the study groups to assess baseline comparability. Continuous variables (e.g., subject age, weight, height, and body mass index (BMI)) will be summarized using descriptive statistics (number [n], mean, standard deviation, and standard error, median, minimum, and maximum). Categorical variables will be summarized using subject counts and percentages. Categories for missing data will be presented if necessary.

3.2.3. Concomitant medication

All concomitant treatments taken during the treatment period will be summarized by treatment in the safety analysis set.

3.2.4. Protocol deviations

A data listing of all protocol deviations will be generated. This listing will be reviewed by the study team and each protocol deviation will be identified as major or minor.

3.3. Efficacy analysis

Efficacy analyses will be carried out in the mITT analysis set by treatment arm.

3.3.1. Primary efficacy hypothesis

The primary hypothesis of this study is that ACP-01 is superior to placebo in terms of the earlier time from treatment with IMP to either de-novo gangrene, or doubling of wound size, or major amputation, or death.

3.3.2. Primary efficacy endpoint

3.3.2.1. Definition

The primary efficacy endpoint for this study is the earlier time from treatment with IMP to either de-novo gangrene in the treated limb, or doubling of wound size in the treated limb, or major amputation in the treated limb, or death. For subjects who were lost to follow-up or completed Month 12 study visit without a study event, the time to event will be censored by the subject's last follow-up date in the study.

3.3.2.2. Primary analysis

The primary efficacy analysis will be the comparison of the distribution of time to event between the two treatment arms using a stratified log-rank test at two-sided 5% level of significance, adjusted by study site and baseline prognostic factors.

The hazard ratio (HR) and its corresponding 95% confidence interval (CI) will be estimated using a stratified Cox proportional hazard (CPH) model. Time to event for each arm will be summarized using Kaplan Meier curves and further characterized in terms of the median and survival probabilities at 3, 6, 9, and 12 months along with the corresponding 2-sided 95% CI for the estimates.

Underlying assumptions of proportional hazards will be checked using Schoenfeld Residuals test and graphical methods (Log cumulative hazard curve). The adequacy of the proportional hazards (PH) assumption will also be confirmed by including a time dependent covariate for the active treatment group by log (time) interaction in the primary analysis model and testing it using 5% significance level. If proportionality is not observed, sensitivity analyses other than those already planned in the SAP could be carried out.

3.3.2.3. Sensitivity analyses

In order to assess the consistency of the primary analysis of time to event, sensitivity analyses will be carried out including:

- An unstratified log-rank test and the hazard ratio along with the associated 95% CI resulting from an unstratified Cox model (only treatment arm in the model).
- An analysis based on PP analysis set

Three additional sensitivity analyses will be performed to assess the robustness of the primary analysis results to the possible violation of the noninformative censoring assumption. The first sensitivity analysis assumes that subjects who discontinued without meeting any of the event criteria during the study had an event instead of being censored. The second sensitivity analysis will be based on the delta-adjusted method examined by Zhao et al. (2014). The third sensitivity analysis is an extension of the placebo-based pattern mixture model proposed by Lu (2014, 2015). The placebo-based pattern mixture model assumes that subjects who discontinued from the ACP-01 arm would have an event after discontinuation similar to that of placebo. The extended placebo-based pattern mixture model uses a sensitivity parameter to characterize the gradual deviation from the noninformative censoring underlying the primary analysis toward the informative censoring underlying the placebo-based pattern mixture model. The extended placebo-based pattern mixture model sensitivity analysis for time-to-event data is described as follows:

Let $h_0(t)$ denote the baseline hazard function associated with the placebo group. Let β_1 denote the treatment effect in terms of log hazard ratios under noninformative censoring for ACP-01 versus placebo. The hazard function associated with ACP-01 under noninformative censoring is thus given by $h_1(t) = h_0(t) \exp(\beta_1)$. Consider the extended placebo-based pattern mixture model sensitivity analysis, for the placebo group, we assume that subjects with premature discontinuation would have comparable experience after discontinuation to their counterparts without premature discontinuation. For the ACP-01 treatment group, each dropout time-point for ACP-01 subjects defines a missing data pattern, and we assume that subjects with premature discontinuation would have an event after discontinuation somewhere between their counterparts without premature discontinuation and subjects in the placebo group. Specifically, we assume that $h_1(t) = h_0(t) \exp((1-\phi)\beta_1)$ for $t > C$, where C denotes the time of premature discontinuation. The sensitivity parameter $\phi \in [0,1]$ characterizes the gradual deviation from the noninformative censoring with $\phi = 0$ toward the informative censoring underlying the placebo-based pattern mixture model with $\phi = 1$. A multiple imputation approach will be used to implement the extended placebo-based pattern mixture model.

Technical details for the implementation of the sensitivity analyses are provided in Appendix I.

3.3.3. Secondary efficacy endpoints

The change from baseline in VAS pain score in the treated limb is defined as the difference between the Last Observed Value (LOV) of an individual subject subtracted from the last measurement taken prior to study IMP administration. Subjects who early terminated from the study or met the study event will be imputed a value according to the worst-case scenario; the worst recorded measurement of change of the entire study population.

The change from baseline in Ulcer Size (cm^2) in the treated limb is defined as the difference between the Last Observed Value (LOV) of an individual subject subtracted from the last measurement taken prior to study IMP administration. Subjects who early terminated from the study or met the study event will be imputed a value according to the worst-case scenario; the worst recorded measurement of change of the entire study population. In addition, Ulcer Size at baseline will be treated as zero if Ulcer is not present.

In order to control the overall Type I error rate for the primary and secondary hypotheses, the following sequential testing procedure will be implemented in the following order:

- Change from Baseline in VAS pain score in the treated limb
- Change from Baseline in Ulcer Size in the treated limb

The model baseline adjusted Least Squares Means (LSM) of the change from baseline to LOV of each of key secondary endpoints will be compared between the two study groups by applying an ANCOVA model. The model will include treatment group, study site and baseline pain measurement or baseline ulcer size measurement.

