### **20.3. Significance Level**

The overall significance level for this study will be 5% using two-tailed tests. The study will have one primary endpoint and 2 secondary end-points ordered in a hierarchy, and analyses will utilize the gatekeeping approach to maintain the experiment-wise type-I error of 5%. The order of the hierarchy of the secondary endpoints testing following the primary end-point testing is as follows:

- Change from Baseline in VAS pain score
- Change from Baseline in Ulcer Size

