### 20.7.2. Key Secondary Endpoint Analyses

#### 20.7.2.a. Change from Baseline in VAS pain score

The change from baseline in VAS pain score is defined at the difference between the Last Observed Value (LOV) of an individual subject subtracted from the last measurements taken prior to study IMP administration. Subjects who early terminated from the study or met the study event will be imputed a value according to the worst-case scenario; the worst recorded measurement of change of the entier study population.

The model baseline adjusted Least Squares Means (LSM) of the change from baseline to LOV of this endpoint will be compared the two study groups by applying an ANCOVA model (SAS® MIXED procedure). The model will include treatment group, study site and baseline pain measurement.

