1.3. Determination of sample size

Sample size calculations were performed under the following assumptions:

- The primary study endpoint is the earlier time from treatment with study IMP to either de-novo gangrene, or doubling of wound size, or major amputation, or death.
- Randomization will allocate subjects to autologous ACPs or placebo using a 2:1 assignment ratio, respectively, stratified by site.
- The expected median time to study event as defined by the primary efficacy endpoint, assuming exponentially distributed time to event, is 3 months for placebo-treated subjects and 7 months for the ACP-treated arm.
- The anticipated monthly randomization and study IMP administration rate is 6 subjects per month.
- The minimal follow-up period of a subject will be 26 weeks if the primary endpoint is not reached, and the maximal follow-up period will be 52 weeks.
- Final analysis, under these assumptions is planned to be conducted at approximately at 22 months from first subject IMP treatment including a total of 95 subjects.
- As the effect of the early futility analysis is marginal, the final analysis will use a two-sided alpha level of 0.05

Under the above assumptions, a total of 95 subjects treated with the study IMP will provide 94% power to detect a statistically significant result at a two-sided alpha level as specified above.

The interim analysis was conducted on clinical data exported 15April2020. At the time of the 15Apr2020 data export, 65 subjects had been enrolled, treated, and followed. Subjects were enrolled in a 2:1 randomization. Follow-up ranged from 1 day to 401 days since treatment. Overall, median time-to-event was 241 days. As far as efficacy, at this stage of the clinical trial, there was not enough evidence to demonstrate that there was a difference between the two treatment groups in either the incidence or the timing of primary endpoint events.

The protocol specified that this interim analysis was to be conducted as a formal futility analysis, however this type of formal analysis was not performed. The results of this interim analysis were considered to be non-conclusive with regards to the futility objective and, therefore, the trial was allowed to proceed.

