With a total of 65 evaluable subjects for final analysis, at least 51 events will be required for final analysis to detect a hazard ratio of 0.43 with 81% power at one-sided 2.5% level of significance, if the median time to study event in the placebo arm is expected to be 3 months. Power is expected to be higher if about 8 patients from South African sites are included.

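### If the event effect is as designed, the worst-value rule in SAP 3.3.3 makes the VAS result mainly an event-rate contrast reported as a mean change, and no own-value check is designated

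*SAP*

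**What the plan says.** - SAP 3.3.3 defines both key secondary endpoints as the treated-limb change from the last pre-treatment measurement to the last observed value. It then adds: "Subjects who early terminated from the study or met the study event will be imputed a value according to the worst-case scenario". The value is "the worst recorded measurement of change of the entire study population". Protocol 20.7.2.a has the same rule for VAS ("the worst recorded measurement of change of the entier study population"), and 20.7.2.b has it for ulcer size.
- The comparison is an ANCOVA with treatment, site and baseline, on the "Least Squares Means (LSM) of the change from baseline to LOV of each of key secondary endpoints".
- For ulcers, "Ulcer Size at baseline will be treated as zero if Ulcer is not present".
- Protocol 20.3 tests VAS and then ulcer size after the primary endpoint: "analyses will utilize the gatekeeping approach to maintain the experiment-wise type-I error of 5" per cent. SAP 3.3.3 keeps that order.
- The sensitivity analyses in SAP 3.3.2.3 concern the primary endpoint only. SAP 3.4 lists Week 13 and Week 26 measures, last-observed responders and a win ratio, all exploratory and without multiplicity control.

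**The concern.** The rule overwrites recorded data: values measured after de-novo gangrene or wound doubling, last values before death or amputation, and everything from early terminators. All these subjects receive one constant, set by the most extreme subject in the study. If most subjects carry that constant, the difference in adjusted means largely reflects the difference in how many per arm carry it, which the primary endpoint has already tested.

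The secondaries are formally tested only after the primary succeeds, so an event difference will then have been observed. A positive VAS test would be reported as a second, multiplicity-controlled finding, in VAS points, when it may mostly repeat the first. For ulcers, a subject with rest pain only (eligible under Protocol 8.1.1) enters at zero and, after dying, is assigned the largest ulcer growth in the study.

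**Working it through.** **1. The plan's own figure.** SAP 1.3 states that "at least 51 events will be required for final analysis to detect a hazard ratio of 0.43 with 81% power" at one-sided 2.5%. With 2:1 allocation, power = Φ(√(51 × 2/9) × |ln 0.43| − 1.96) = Φ(3.367 × 0.844 − 1.96) = Φ(0.88) = 81%. This reproduces. The 51 of 65 is a power requirement, not a forecast, so it is not used below.

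**2. Share of subjects with an event.** Inputs from SAP 1.3: medians 3 and 7 months, exponential times, 2:1 allocation. Share = 1 − 2^(−t/median).

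| | Placebo | ACP-01 | Pooled |
|---|---|---|---|
| Planning medians, 12 months | 93.8% | 69.5% | 77.6% (50.4 of 65) |
| From the 241-day median, 12 months | 83.7% | 54.0% | 63.9% (41.5 of 65) |
| Planning medians, 6 months | 75.0% | 44.8% | 54.9% |
| From the 241-day median, 26 weeks | 59.5% | 32.1% | 41.2% |

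For the interim rows, SAP 1.3 reports: "Overall, median time-to-event was 241 days". Taking 241 days = 7.92 months as a pooled median and assuming HR 3/7, solve (1/3)e^(−7.92λ) + (2/3)e^(−(3/7)7.92λ) = 0.5. The medians are 4.59 months (placebo) and 10.71 months (ACP-01). Early terminators add to all these shares.

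**3. What the difference in means consists of.** Let f be the share given the worst change W, and m the mean change in the other subjects (P placebo, A ACP-01). Ignoring the baseline adjustment:

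benefit = (f_P − f_A)(W − m_P) + (1 − f_A)(m_P − m_A).

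The first term is events and the second is measured change. With no pain effect the second is zero, and the first is 0.242(W − m_P) on planning rates or 0.297(W − m_P) on interim rates.

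**4. VAS simulation.** 65 subjects (43:22), 12 months, 10,000 trials per cell; the HR 0.7 row was run separately with fewer trials. The documents give no VAS distribution, so these inputs are assumed: scale 0-10, baseline mean 6 (SD 2), mean change −1, change SD 2.5, pain independent of events, no dropout and no site term. Change is last minus baseline, so negative is benefit. Entries are the percentage of trials favouring ACP-01 at two-sided 5%, planning / interim event rates.

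| Scenario | Planned rule | Own last values |
|---|---|---|
| HR 3/7, no pain effect | 54 / 56 (mean −1.24 / −1.52 points) | 2.6 / 2.7 |
| same, given a significant log-rank | 63 / 69 | – |
| HR 0.7, no pain effect (placebo median held) | 7 / 13 (mean −0.4 / −0.6) | – |
| HR 3/7, true 2-point benefit | 69 / 79 | 82 / 82 |
| Equal event rates (77.6% / 63.9%), true 2-point benefit | 5 / 9 | 82 / 82 |
| Equal event rates, no pain effect | 1.7 / 2.1 | – |

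In the equal-rate rows the formal VAS test is reached in only about 3% of trials, because the primary rarely succeeds.

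**5. Checks on the first row.** Ten sites in the model (number assumed): 54 / 56. With 73 subjects: 60 / 61. Change SD 1.5-3.0: 54-57. If 10% of event-free subjects leave early: 48 / 50; if 20%: 41 / 43. If events themselves worsen pain by 2 points: planned 58 / 59, own values 10 / 12.

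**6. Ulcer size, scale only.** With mean own change zero, the event term is 0.242W to 0.297W. For an assumed worst growth of 10 cm² that is 2.4-3.0 cm²; for 40 cm² it is 9.7-11.9 cm². Protocol 8.1.2 excludes severe ischaemic ulcers above 10 cm² at entry. No rejection rate was simulated.

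**The case against.** The strongest defence is that this is a declared composite. The rule is prespecified, identical in protocol and SAP, and stands beside each endpoint definition. A reader might infer that it breaks type I error control or the gatekeeping. It does neither: with no difference in events or pain, the planned test favours ACP-01 in about 2% of trials, below the nominal 2.5% per side. That part of the defence stands.

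A reader might also infer that the secondaries are an event contrast whatever the drug does. That is too strong. It depends on the design effect, and SAP 1.3 says the interim data did not show a difference in events. At HR 0.7 most of the effect disappears, and the test does respond to a real pain benefit (69-79% against 54-56%).

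Four further points stand in part:
- The 64% end assumes that 241 days is a pooled survival median, which SAP 1.3 does not specify. SAP 1.3 also allows 26-week minimal follow-up, although SAP 1.2 plans 52 weeks for all treated subjects.
- Pain is unlikely to be independent of gangrene or amputation. If events worsen pain by 4 points, own values themselves favour ACP-01 in 23 / 29% of trials, so part of the contrast would be real; the planned rule remains higher, at about 61%.
- A reader might carry the VAS error rate over to ulcer size. Nothing shown supports that: wound doubling is itself ulcer growth, so part of the imputed difference is genuine ulcer information.
- The plan is not silent on measured values, because SAP 3.4 summarises several. But none is named as a check on these two tests.

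**Conclusion.** The concern holds in conditional form. The event share of 64-78% over 52 weeks (41-55% at 26 weeks) follows from the documents' medians, exponential times and, at the lower end, an assumed HR of 3/7. It needs no pain data. If the event effect is as designed, the VAS difference is driven mainly by events: a drug without any pain effect would show a benefit in about 54-56% of trials under the assumed VAS values. If event rates are equal, the rule hides a true 2-point benefit. In either case one extreme subject sets the size of the estimate, so reading it as points or cm² is not justified. For ulcer size the conclusion is limited to scale.

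This is a fault of labelling and of a missing supporting analysis, not an invalid test. It should be corrected, because a positive result as planned could not show on its own whether pain or ulcer size changed beyond the event effect.

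**What to change.** Amend SAP 3.3.3 before unblinding. The sponsor may keep the current rule as the main analysis.

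1. Add a prespecified sensitivity analysis of each key secondary using each subject's own last observed treated-limb value. Include values recorded after de-novo gangrene or wound doubling; if there are none, use the last one before the event. Give the worst rank to death and to major amputation of the treated limb. Use a rank ANCOVA (treatment, site, baseline) or a site-stratified Wilcoxon test. Show early terminators without an event both ways: own last value and worst case.
2. Report by arm how many subjects received the worst value.
3. Describe the worst-value result as a composite of events and pain or ulcer status. Claim an effect on pain or ulcer size itself only if the own-value analysis supports it.

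The cost is modest extra analysis and a more restrained secondary claim. Values after an event may be sparse, because the minimal follow-up is stated only for subjects who have not reached the endpoint.

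Making the rank test the main analysis is optional, because it trades power. With HR 3/7 and a true 2-point benefit it has 58-68% power if 25% of events are death or amputation, and 43-60% if 50% are, against 69-79% now. It also still reflects events in part: with no pain effect it favours ACP-01 in 6-7% and 13-17% of trials respectively. Those event shares are assumed; the documents do not give them.

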3.3.4. Subgroup analyses

Time to event subgroup analyses are planned to further explore the homogeneity of the treatment effect across patient subsets. Depending on the sample size, the subgroups, as defined in section 2.3 will be examined.

An unstratified Cox-regression model with treatment arm as predictor variable will be fitted separately for each subgroup category. The hazard ratio for treatment along with the associated 95% confidence interval will be provided.

Forest Plot of Hazard Ratios for treatment effect on time to event by selected subgroup will be provided.

The same subgroup analyses will be done for the two key secondary endpoints.

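### The subgroup plan (SAP 3.3.4) sets out to explore homogeneity of the treatment effect but specifies no estimate of the difference between categories; adding one is cheap.

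*SAP*

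**What the plan says.** SAP 3.3.4 gives the purpose of the time-to-event subgroup analyses as "to further explore the homogeneity of the treatment effect across patient subsets". The method is: "An unstratified Cox-regression model with treatment arm as predictor variable will be fitted separately for each subgroup category". The output is a hazard ratio with 95% confidence interval for each category and a forest plot, and the same is to be done for the two key secondary endpoints. SAP 2.3 names region, race, gender, age and baseline prognostic factors, with presence of ulcers and ulcer size as examples. That makes at least six factors, to be examined as the sample size allows.

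Neither the SAP nor protocol section 20 specifies a treatment-by-subgroup term, a heterogeneity test or a rule for reading differences between categories. The only interaction in either document is treatment by log(time), used to check proportional hazards (SAP 3.3.2.2, protocol 20.7.1). The ANCOVA for the secondaries (SAP 3.3.3) contains treatment, site and the baseline value only.

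**The concern.** Homogeneity is a statement about the difference between categories. Separate models estimate the effect within each category and leave that difference unestimated. A reader who meets a forest plot without it may fall back on noting which intervals cross 1. In a trial of this size each category has modest power, so one interval can exclude 1 and the other include it even when the true effect is identical. At stake is how the subgroup results are interpreted, not the primary or secondary tests.

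**Working it through.** **Inputs from the documents**
- Events, effect and power (SAP 1.3): "at least 51 events will be required for final analysis to detect a hazard ratio of 0.43 with 81% power at one-sided 2.5% level".
- Allocation (SAP 1.3): "Subjects were enrolled in a 2:1 randomization", so the allocation factor is 2/3 × 1/3 = 2/9.
- Level (SAP 3.3.2.2): two-sided 5%, critical value 1.96, the same as one-sided 2.5%.

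**Assumption.** The documents give no subgroup sizes. I take a two-category factor with events split 50:50, 70:30 or 80:20.

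**Step 1: reproduce the SAP's power.** Power = Φ(√(d × 2/9) × |ln HR| − 1.96), where |ln 0.43| = 0.844. For d = 51: √11.33 = 3.367; 3.367 × 0.844 = 2.841; Φ(0.881) = 0.811. This matches the stated 81%.

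**Step 2: power within a category, uniform HR 0.43**
- 50:50, d = 25.5 each: √5.667 = 2.380; 2.380 × 0.844 = 2.009; Φ(0.049) = 0.52.
- 70:30, d = 35.7 and 15.3: Φ(2.377 − 1.96) = 0.66 and Φ(1.556 − 1.96) = 0.34.

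**Step 3: chance that exactly one interval excludes 1** = p1(1 − p2) + p2(1 − p1)
- 50:50: 2 × 0.52 × 0.48 = 0.50.
- 70:30: 0.66 × 0.66 + 0.34 × 0.34 = 0.55.
- 80:20: powers 0.72 and 0.25, giving 0.61.

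A Cox simulation (65 subjects, 2:1, placebo median 3 months, 12-month cap) gave 48.5%, 57% and 63% for the three splits.

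**Step 4: dependence on the true uniform HR** (51 events, 50:50, both tails counted)

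| HR | Power per category | Exactly one excludes 1 |
|---|---|---|
| 0.43 | 52% | 50% |
| 0.6 | 23% | 35% |
| 0.8 | 8.3% | 15% |
| 1.0 | 5% | 9.5% |

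**Step 5: dependence on how the plot is read** (HR 0.43, 50:50)
- Hazard ratios on opposite sides of 1: P(one category above 1) = Φ(−2.009) = 0.022; 2 × 0.022 × 0.978 = 4.4%.
- Non-overlapping 95% intervals: 2 × (1 − Φ(2 × 1.96/√2)) = 0.6%.

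**Step 6: when the overall result is significant.** Under the same normal approximation, and given an overall two-sided p below 0.05, discordance with a uniform effect is 57% (50:50) and 63% (70:30) at HR 0.43, and 66% and about 69% at HR 0.6. At HR 0.43, without that condition, only about 8% to 10% of discordant pairs would also have an interaction p below 0.05.

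**Step 7: what an interaction estimate can deliver** (51 events, 50:50). Variance of each log HR = 1/(25.5 × 2/9) = 0.1765. SE of the log ratio of HRs = √(0.1765 + 0.1765) = 0.594. Power for a two-fold ratio = Φ(0.693/0.594 − 1.96) = 0.21. The ratio needed for 80% power = exp((1.96 + 0.842) × 0.594) ≈ 5.3.

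**The case against.** Four points on the other side carry weight.

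1. **The aim is modest.** The SAP says explore. Subgroups lie outside the testing sequence, and no subgroup p-value or significance rule is planned. A reader might infer that the analysis is meant to demonstrate homogeneity; the text does not say so. This stands, but an exploratory analysis should still estimate the quantity it names.

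2. **The comparison can be recovered.** Categories of one factor are disjoint sets of subjects. A ratio of hazard ratios and an approximate heterogeneity test therefore follow from the reported intervals (SE = width of the log interval / 3.92). It would be too strong to say that the planned output cannot be used to assess homogeneity, or that readers can only look at which intervals cross 1. What stands is that the plan leaves the calculation to the reader.

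3. **The 50% is conditional.** A reader might infer that a uniform effect will look heterogeneous about half the time in general. That needs a true hazard ratio of 0.43, about 51 events, two categories, an assumed split and a significant/non-significant reading that the SAP does not prescribe. For a 50:50 split, 2p(1 − p) cannot exceed 50%, so the design value sits at the ceiling. SAP 1.3 also reports an overall interim median of 241 days and no demonstrated difference between arms. The design medians of 3 and 7 months at 2:1 imply a pooled median of about 5.2 months, or roughly 158 days. This does not exclude 0.43, but it argues for showing a range. Step 6 limits how much comfort smaller effects give: in a positive trial, discordance is more frequent at 0.6 than at 0.43.

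4. **Interaction p-values can mislead too.** With six factors at 5% each, the chance of at least one false positive is 1 − 0.95^6 = 26%. Over three endpoints (18 tests) it is 1 − 0.95^18 = 60%, if the tests are independent, which they will not be. This stands, and the fix must say how such p-values are to be read.

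**Conclusion.** The point holds as a cheap improvement of low severity. The plan names homogeneity as its subgroup question and specifies no between-category estimate for any of the three endpoints.

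Its practical size depends on the reading rule and the true effect. If intervals are compared for excluding 1, discordance under a uniform effect is 50% to 55% at the design hazard ratio (50:50 to 70:30 splits, both assumed). At 50:50 it drops to about 10% as the hazard ratio approaches 1. Judged by direction or by interval overlap, it is rare.

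A reader might go further and infer that a claim of benefit in one subgroup and not another is planned. No section of either document plans one.

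**What to change.** In SAP 3.3.4, for each factor fit one model with treatment, factor and treatment-by-factor: Cox for the primary endpoint, the existing ANCOVA plus these terms for the secondaries. Put the ratio of hazard ratios, or the difference between categories in the LS mean treatment effect, with its 95% interval on the forest plot. Keep the per-category estimates as display.

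Add three statements:
- Statistical significance within categories will not be compared.
- Any interaction p-values are exploratory and unadjusted over at least six factors and three endpoints.
- Precision is low: about 21% power for a two-fold ratio of hazard ratios with 51 events split 50:50.

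The cost is a little more programming and wide interaction intervals. That width tells readers that data of this size can neither establish nor exclude moderate heterogeneity.
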